Figure 1: Examples of prostheses that may be compared in the experiment: energy storage-and-return prostheses (ESR, left); ESR with passive hydraulic ankle (PHA); and ESR with microprocessor-controlled ankle (MPA). Examples shown are Endolite Esprit, Echelon, and Élan. Specific prostheses from multiple manufacturers will be chosen in the course of the research.

Experiments will use standard commercially available prostheses for persons with lower-limb amputation. Specific prostheses will be determined at the time of the study, but they will include prostheses that are fully passive such as energy storage-and-return (ESR) feet, ESR feet with mobilized ankles such as passive hydraulic ankles (PHA), and ESR feet with microprocessor-

controlled ankles (MPA). Examples from one manufacturer (Endolite) are shown in **Figure 1**. A separate branch of the study will use multiple pre-scribed prostheses that an individual already possesses – specifically a daily-use prosthesis, a running-specific prosthesis, and any other prostheses (including but not limited to activity-specific prostheses). For orthosis users, standard commercially-available orthoses or standard-of-care custom orthoses will be used, as well as a standard commercially-available electrical stimulation neuro-orthosis (BioNess –**Figure 2**). For persons without impairment, different footwear will be used. Each person will use two or more different prostheses or orthoses in the lab and in periods of one to three weeks of everyday life.

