The target enrollment is 20 persons with transtibial amputation and 10 persons with drop-foot at UW-Madison, and up to 20 healthy controls to test the methods. Additional participants with transfemoral amputation (up to 10) may also be enrolled at UW-Madison. Additional participants with transtibial and transfemoral amputation will be recruited at the remote site for a separate data pool (Walter Reed National Military Medical Center, WRNMMC). All subjects will be 18-75 years old, representing the main target population for whom these devices could improve daily life.

We will recruit subjects following inclusion and exclusion criteria mentioned below.

Target Populations:

- The first target population is persons with lower-limb amputation who use prostheses for ambulation.
- The second target population is persons with drop-foot.
 - A targeted subset of the drop-foot population will be persons with Multiple Sclerosis and currently drop-foot.

Inclusion:

Target Populations:

- Subjects will be age 18-75 years at time of enrollment.
- Subjects with amputation must have used a prosthesis for more than 6 months, and wear it for at least 8 hours per day.
- Subjects must be more than 6 months past their most recent surgery (if any).
- Subjects must be free of musculoskeletal and cardiovascular conditions that would limit their ability to safely complete testing.
- Subjects should consider themselves in good health; be able to wear their prostheses or orthoses all day long; be able to perform all of their activities of daily living (ADL) with their prostheses or orthoses as appropriate, have a comfortably fitting functional prosthesis (if applicable) that does not cause any skin problems; and have a stable residual limb (or impaired limb).
- Subjects may use a narrow-base cane (single point, narrow tripod base, etc.) as an ambulatory aid but not a small-base quad cane, wide-base quad cane or walker.
- Subjects must be able to walk with their prostheses or orthoses for 30 minutes (total) and stand for 30 minutes (total), in individual bouts of at least 7 minutes, without becoming fatigued, feeling dizzy, having chest pain or shortness of breath, or experiencing claudication symptoms.
- Subjects most report an estimated average daily walking time of at least 45 minutes outside of the home. This does not need to be continuous and considers walking for all purposes.

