Specific Procedures – Comparing Prostheses and Orthoses using Real-World Data

Study Design:

Subjects will wear one or more movement sensors on various body segments, especially the foot, as well as means of logging location data (e.g. a GPS, Bluetooth, Wifi receiver and/or cell phone app). Subjects will wear (movement sensors) and/or carry (phone) these sensors during extended measurement periods of up to three weeks per experimental condition, for up to four conditions (prostheses, orthoses or footwear). We will combine movement and location data to identify the most-frequently-repeated paths a person takes, and finally analyze movement along these paths to identify changes in mobility performance (**Figure 6**). We will also perform standard biomechanical analyses of posture and movement in the laboratory.

NOTE: Because part of this study is the development of these methods, we may change the number of sensors, which sensors are used, how they are worn/carried, how long the take-home tests are, the devices under study, and other details of the study, within the limits approved in the *Study Procedures – General* section of this protocol.

[figure not shown]

Figure 6: Example self-test by the experimenters showing highly repeated straight walking trajectories found from a 10-day walking test. The experimenter wore athletic shoes and sandals for 5 days each, indicated by solid lines and dashed lines respectively. The same color indicates same paths. Blue and red lines are walking trajectories in the hallway between the subject's office and the restroom and water fountain (different directions are separated into two different paths). Yellow lines represent the sidewalk between the building where the subject works and a nearby bus stop. Purple lines represent a sidewalk between the same building and a dining location.

Test Conditions:

- Prosthetics branch 1: Participants with amputation will use 2-4 prosthetic feet from different categories, each fit to their standard socket by a professional prosthetist.
 - Participants will use each prosthesis for a take-home test of 1-3 weeks of everyday life. Comparisons will include energy-storage-and-return prostheses (ESR) vs. prostheses with a passive hydraulic ankle (PHA) vs. prostheses with a microprocessor ankle (MPA) (**Figure 1**). Comparisons may also include Articulated ESR (AESR) prostheses, which have one or more additional joints in the mechanism, or other types of standard commercial prostheses.

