- Most likely measurements include: miniature inertial sensors, GPS, Bluetooth and Wifi location from a wearable receiver or cell phone app, force plate/force treadmill, EMG, motion capture, indirect calorimetry, and voice/photo/video recording.

Intended Outcome - Primary:

The primary outcome is the measured difference in stride length at identical walking speed when using different prostheses, orthoses, or footwear. We expect to observe increased stride length when using more compliant prostheses or the FES neuro-orthosis.

Intended Outcomes - Secondary:

The secondary outcomes include other measures of gait performance determined from the same system. Stride width, stride clearance, speed, stride frequency, ground reaction forces, and measures of gait regularity are among many analyses that will be performed with the data from this experiment.

Data and Safety Monitoring Plan

The PI will oversee compliance with the data and safety monitoring plan to ensure adherence to IRB guidelines. All researchers and research staff involved in the study are required to maintain Human Subjects and HIPAA training and will be continuously involved in data and safety monitoring. Data and safety monitoring will occur on a continuous basis.

Adverse events or problems will be reviewed by the principal investigator as they occur and reported to the IRB in accordance with posted guidelines at the “Events Requiring Reporting to the IRB” page: <https://kb.wisc.edu/hsirbs/18324>.

Data Processing/Data Analysis:

Electromyographic, kinematic, kinetic, and metabolic data will be compared with different lower limb prostheses, orthoses and footwear, using repeated measures ANOVAs. In initial experiments measuring movement performance with only the subject’s own devices, we will use repeated measures ANOVAs to compare performance variables (e.g. EMG amplitude, gait economy, joint range of motion, peak ground reaction force) under different conditions (e.g. locomotion speed, incline, motor task). Corrections for multiple comparisons will be made using False Discovery Rate adjustments [51], [52]. In analysis of experimental conditions, we will use the new methods developed in this research for analyzing the same types of movement information, isolated to frequently-repeated paths in everyday life. We may also analyze specific events of interest such as slips, trips or falls that occur in everyday life and are recorded by the wearable sensors [53].

Sample size

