For specific tests with a goal of publication, the sample size will be 10 participants. Studies with between 6 and 12 participants are common in the field, and have proven sufficient to

demonstrate many effects in a variety of studies of gait mechanics in persons using prostheses and orthoses [19], [54]–[61]. We estimate sample size from data on changes in gait mechanics across conditions with a past novel prosthesis [54], [56].

The sample size required per group is computed using the following formula:

$$N \text{ (per group)} = 2 * ((z(1-\alpha/2) + z(\beta)) * \sigma / d)^2,$$

where d is the expected difference in outcome value, post- vs. pre-training; σ is the estimated standard deviation; α is the alpha error we would like to control; and β is the statistical power. Here we set a statistical goal of 80% power ($\beta = 0.80$, $z(\beta) = 0.84$) and α level 0.05 ($z(1-\alpha/2) = 1.96$).

Based on changes gait mechanics with a past novel prosthesis, we expect: a difference in ankle push-off of 3.1 ± 1.5 J across several conditions [54], or a difference in opposite-leg collision work of 0.055 ± 0.04 J/kg [56]. These give sample size estimates of 4, and 9 subjects, respectively. This sample-size estimate is conservative, as it uses a two-tailed test when in fact we expect to test for specific changes (one-tailed test), and it does not account for repeated-measures structure in our experimental design. Therefore we expect 6-10 subjects to provide sufficient statistical power. We plan to use 10 subjects for the tests of prostheses and orthoses at UW Madison.

Analysis of Remotely-Collected Data

Data from UW-Madison studies, and separately from WRNMMC studies, will be analyzed at both sites, but primarily UW-Madison. Data from in-lab biomechanics studies as well as take-home studies with wearable sensors will be transmitted between sites. Personnel at both sites may be involved in analyzing the biomechanical data (movement patterns, joint loads, etc.) and interpreting the location-based data (e.g. speed, stride length, limb load) recorded from everyday life. Data transmission will use HIPAA-compliant Box folders, HIPAA-compliant folders on UW's Campus Computing Initiative (CCI) systems, or other HIPAA-compliant means approved by the DOD. Only coded data will be transmitted; each site will retain the only copy of its respective code key linking subject numbers to their direct identifiers, and the other site will not receive this information.

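### Ten participants do not guarantee enough users for each pair of prosthetic feet, because each may use only two of the three types compared; a mixed model and an N stated per pair would close the gap

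*Combined protocol and SAP*

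**What the plan says.** All references are to the combined protocol and SAP.

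- **Sample size.** "For specific tests with a goal of publication, the sample size will be 10 participants". A per-group formula is applied to two reference effects: "These give sample size estimates of 4, and 9 subjects, respectively". The section calls this conservative because it is two-tailed and ignores the repeated-measures structure. It concludes that 6 to 10 subjects should suffice, and adds: "We plan to use 10 subjects for the tests of prostheses and orthoses at UW Madison".
- **Test Conditions, prosthetics branch 1.** On the number of feet per person, the rule reads: "Participants with amputation will use 2-4 prosthetic feet from different categories, each fit to their standard socket by a professional prosthetist". Of the devices it says "Comparisons will include energy-storage-and-return prostheses (ESR) vs. prostheses with a passive hydraulic ankle (PHA) vs. prostheses with a microprocessor ankle (MPA"; articulated ESR feet or other types are optional.
- **Research Design and Methods.** "Each person will use two or more different prostheses or orthoses in the lab".
- **Data Processing/Data Analysis.** "Electromyographic, kinematic, kinetic, and metabolic data will be compared with different lower limb prostheses, orthoses and footwear, using repeated measures ANOVAs". The factor levels are not given, and there is no rule for a participant who did not use one of the devices. For the experimental conditions the section also refers to new methods based on frequently repeated paths.
- **Target Population and Enrollment.** "The target enrollment is 20 persons with transtibial amputation and 10 persons with drop-foot at UW-Madison". How the 20 divide between the two prosthetics branches is not stated.

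**The concern.** A sample size for a within-person comparison counts the people who contribute to that comparison. Ten people support each of ESR vs. PHA, ESR vs. MPA and PHA vs. MPA only if all, or nearly all, of them use all three types. The plan compares three types, allows two per person and sets no minimum per pair. The number behind a given contrast can therefore be well below ten with the protocol fully followed.

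The named analysis may add to this. A classical repeated measures ANOVA with three device levels uses only participants who have all three, so data from those with two feet would be lost. Comparing prosthetic foot-ankle systems is the primary objective, so these are the contrasts that matter most.

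**Working it through.** **Inputs.** From Sample size: push-off work 3.1 J, SD 1.5 J; collision work 0.055 J/kg, SD 0.04 J/kg; alpha 0.05; power 80%; N = 10. From Test Conditions: 2 to 4 feet per participant, three types compared. The within-person correlation and dropout are not stated; dropout is taken as 0.

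**1. The plan's own figures.** N per group = 2 × ((1.96 + 0.84) × σ/d)².
- Push-off: 2 × (2.8 × 1.5/3.1)² = 3.67, rounded up to 4.
- Collision work: 2 × (2.8 × 0.04/0.055)² = 8.29, rounded up to 9.

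Both reproduce.

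**2. Users per pair.** Ten participants with two of three feet each, spread evenly, divide 4/3/3 over the three pairs. Each foot then has 6 or 7 users and each pair 3 or 4. If k of the ten use all three feet, the smallest pair has k + floor((10 − k)/3) users. That reaches 6 at k = 4 and 7 at k = 6.

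**3. Power per pair.** Paired t-test, n − 1 degrees of freedom, non-centrality (0.055/0.04) × √n = 1.375√n. Here 0.04 is taken as the SD of differences, which equals a per-condition SD of 0.04 with correlation 0.5.

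| Users per pair | Two-sided 0.05 | One-sided 0.05 |
|---|---|---|
| 3 | 28% | 47% |
| 4 | 47% | 67% |
| 5 | 64% | 81% |
| 6 | 77% | 89% |
| 7 | 86% | 94% |
| 10 | 97% | 99% |

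The 80% goal is reached at 7 users two-sided and at 5 one-sided. For push-off (3.1/1.5), two-sided power is 49% with 3 users and 78% with 4.

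**4. Sensitivity to correlation.** If 0.04 is instead a per-condition SD, the SD of differences is 0.04 × √(2(1 − ρ)). Two-sided power with 3 and 4 users is:
- ρ = 0: 17% and 28%
- ρ = 0.3: 22% and 37%
- ρ = 0.7: 40% and 66%
- ρ = 0.8: 52% and 82%

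**5. What the model choice does on the same 4/3/3 split.**
- Classical ANOVA with three device levels: 0 of 10 participants are complete.
- Linear model with device and participant effects: each contrast combines its direct pairs with the indirect route through the third foot. For the pair with 4 users, 4 + 1/(1/3 + 1/3) = 5.50 effective pairs. For each pair with 3 users, 3 + 1/(1/4 + 1/3) = 4.71. Error degrees of freedom are 20 observations − 10 participants − 2 device contrasts = 8. With non-centrality 1.375 × √(effective pairs), two-sided power is 81% and 74%.

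**6. If all 20 transtibial participants were in branch 1 with two feet each.** Each pair has 6 or 7 users, giving 77% to 86%.

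**The case against.** Several points on the other side are sound.

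- **A reader might infer that the plan requires 9 per comparison and that ten participants miss it.** The documents do not support that. The 9 is a per-group figure from an independent-groups formula, and the plan itself calls it conservative and settles on 6 to 10. The relevant thresholds are the plan's floor of 6, or the 7 (two-sided) or 5 (one-sided) from the paired calculation. Three or four users fall short of each of these.
- **A reader might infer that the stated ANOVA would have no usable participants.** The plan states neither a three-level factor nor a complete-case rule; a separate two-level ANOVA for each pair fits the wording equally well. The loss follows only if all three feet are entered as levels in a classical analysis. Everyday-path data may be analysed by the new methods instead.
- **The two-foot split is constructed.** No incomplete allocation is described. Ten could mean ten for each specific test, or the target of 20 could supply ten per branch with all feet used. The section on the relationship between UW and WRNMMC gives one-week periods at UW. Payment of up to USD 360 at USD 90 per week is 360/90 = 4 weeks, which fits four one-week conditions. It also fits two feet for two weeks each, since Test Conditions allows 1 to 3 weeks per device.
- **The UW work is described partly as pilot testing for methods development.** That lowers the stakes, although the primary objective remains the comparison of feet.

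These points make the low figures less likely. They do not supply the missing statement of how many participants stand behind each contrast.

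**Conclusion.** The point holds as a gap between what the design permits and what the sample-size statement assumes. At the permitted lower bound, each pair of feet has 3 or 4 users and 28% to 47% two-sided power for collision work (47% to 67% one-sided), against a goal of 80%. If all ten use all three feet, power is 97% and nothing is wrong.

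The low figures rest on four assumptions: every participant uses exactly two feet, only ten enter branch 1, 0.04 is the SD of differences, and the analysis uses only people who wore both feet of a pair. They describe collision work, because the plan gives no difference or SD for stride length, the primary outcome under Intended Outcome.

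Two further inferences should be avoided. This is not an arithmetic error, since 4 and 9 are correct. Nor do the documents show that the study will be underpowered, because the split is a lower bound and not a forecast. The orthotics branch is unaffected, since each participant there has both devices. The improvement is modest but worth making.

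**What to change.** 1. In Data Processing/Data Analysis, replace repeated measures ANOVA for device comparisons with a linear mixed model (device fixed, participant random) and a small-sample degrees-of-freedom method. Participants with two of the three feet then contribute to every contrast, and power on the 4/3/3 split is 74% to 81% under the assumptions above. The cost is small: a different model on the same data, with the usual assumption that which feet a participant used is unrelated to outcome given the model.

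2. In Sample size, say that the 10 and the 80% goal apply to each device pair only if participants use all the feet compared. Otherwise give the expected number of participants per pair and the resulting power. This is a text change. If the answer is that all ten use every foot compared, participants who would have used two take on extra device periods, and some people may not be able to take part. If the flexibility is kept, precision per contrast is lower: 4.7 to 5.5 effective pairs in place of 10 on the split above.

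Stating how the 20 transtibial participants divide between the two prosthetics branches would make the second change easier to write.
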